6.4.4 Neuropsychological Screening Assessment – ABNAS

Neuropsychological function will be assessed with the ABNAS (Aldenkamp and Baker Neuropsychological Assessment Schedule). This is a patient completed assessment of cognitive impairment and function based on everyday activities, that takes approximately 5 minutes to complete (26). This has been used in epilepsy and a range of other conditions with neuropsychological impairment, and has normative data available, but has not been used previously in meningitis. ([name], Prof of Neuropsychology, Liverpool is advising on this aspect of the study.)

6.4.5 Amendment 09 (17/09/2012)

Early analysis has shown that there is no difference between the control patients and the viral meningitis patients (n=20 in each group). Therefore, it is postulated that as our control patients are patients that have been hospitalised a more 'healthy' control group is needed. Therefore, we will ask the participants when they are filling in the questionnaires to also give a pack of questionnaires to a relative/friend/neighbour to also fill in and return. Data on age and gender will be collected on these healthy controls.

The HIT, SF-36, ABNAS, and EQ-5D will be performed at 6, 12, 24 and 48 weeks after discharge. Each of these is a patient self-completed questionnaire which collectively will take twenty to thirty minutes to complete. It is important to obtain these serial evaluations so that we can determine the best endpoint for the subsequent treatment study.

6.4.6 Substantial Amendment 17 (01/05/2015)

Some patients will be sent an additional questionnaire 2 years after discharge to monitor the significant differences observed at the 48 week time point. From May 2015, the TMS and follow-up questionnaires will no longer be given, or sent, to new patients enrolled on the study.

6.5 Loss to Follow – Up

Two written attempts and one phone call will be made to follow up patients before a patient is defined as lost to follow up.

6.5.1 Amendment 12 (3/9/2013)

An interim analysis of the questionnaire responses has shown various areas in need of change:

1) Patient will be contacted by telephone at 6 weeks and one year if they have not responded to the questionnaires to ask for their responses over the phone. This will, hopefully, increase the response rate.

Time off work was an important area that had not been considered, therefore:

2) An additional thank you letter will be sent with the final set of questionnaires with a question enquiring about the amount of time spent off work.

3) A question will be added to the economic questionnaire to enquire about amount of time spent off work.

The HIT questionnaire was confusing for patients who have never suffered headaches.

4) A statement will be added to the covering letter that states 'if you do not suffer from headaches please tick NEVER for all the questions on the HIT'. This is because some patients are doing this and some are leaving blank and some are not returning the questionnaires.

6.6 Study Closure

Study recruitment will finish one year after the study period begins. The study will close when all the follow up from those patients has been achieved – approximately one year after that.

6.6.1 Extension (14/01/2015)

The study was extended until 31 December 2015

6.6.2 Non-substantial amendment 19 (25/11/2015)

The study was extended until 01 October 2016.

6.7 Schedule

	Who?	Baseline	Post LP	Daily for 3 weeks from admission	6 weeks (+/- 1 week)	12 weeks (+/- 1 week)	24 weeks (+/- 1 week)	48 weeks (+/- 1 week)
Consent Form	LC/RN	X						
Assessment of eligibility criteria	LC/RN	X						
Review of medical history	RN	X						
Ask re oral/genital ulcers (if not documented in medical history)	RN	X						
Check routine bloods taken (FBC, clotting, U and E's, LFTs, CRP, glucose, blood cultures)*,	RN	X						
Throat Swab for enterovirus PCR	CT							
Blood for proteomics and genomics (SST and PAXgene™ tube to be supplied by BIUK)	CT/RN	X						
Stool sample for enterovirus PCR	CT/RN	X						
If oral/genital/skin lesions present. Swab of oral/genital/skin lesion for HSV/VZV PCR Any vesicles present should have fluid sent for HSV, VZV, enterovirus and parechovirus PCR	CT	(X)						
Lumbar puncture***	CT	X						
If no self reported/documentated genital lesions. Self taken genital swab for HSV if CSF positive for HSV. Women – vulval, vaginal and perianal swab. Men – perianal and penile skin swab.	RN/Patient		(X)					
Meningitest performed	RN/RF		X					
Charlson Index	RN/RF	X						
TMS	Patient/RN/RF			X				
HIT	RN/RF				X	X	X	X
ABNAS	RN/RF				X	X	X	X
EQ5D	RN/RF				X	X	X	X
SF36	RN/RF				X	X	X	X

(X) If appropriate

* If not performed already these should be taken

** One for HSV type specific serology if needed and one for proteomics and genomics work

***Opening pressure, protein, glucose, cell count, microscopy and culture, PCR as appropriate for cell count/clinical judgement, stored

sample for proteomics/genomics. LC= Local collaborator, CT= Clinical team, RN = Research Nurse, RF= Research Fellow

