- Any vesicle fluid present will be tested for HSV, VZV, enterovirus and parechovirus (if available locally).

Again these samples are considered to be good practice and are reiterated in the Health Protection Agency's Standard Operating Procedure 48 (The investigation of viral encephalitis and meningitis.)

In those with proven **HSV meningitis**

- If self reported genital lesions present swab as above.
- HSV type specific serology at time of presentation
 - If type specific serology is IgG negative then further follow up type specific serology will be requested at 6 months to document seroconversion.(this can be done by the research nurse or fellow at the patient's home)
- If no genital lesions self reported participants will be asked to self swab for asymptomatic genital HSV infection as follows:
 - Men – swab penile skin and perianal area.
 - Women – swab vaginal, vulval and perianal area.

(Different swabs can be used for the different areas but all the swabs will be put into the same vial of transport medium.)

In order to find out if there is a link between genital HSV infection and undiagnosed aseptic meningitis we will also ask **all patients in the aseptic meningitis** group to take genital swabs, as above. We will advise these patients that if their swabs return positive we will contact them and suggest self referral to a local sexual health clinic. Currently the relationship between viral shedding and incidence of meningitis is unknown. We know from enterovirus infection of the CNS that we can find the virus outside of the CNS when it is not demonstrable in the CSF.

If a patient lacks capacity genital swabs will NOT be taken unless clinically indicated.

To facilitate in collection of the appropriate samples we will, where they are in place, use the pre – prepared lumbar puncture packs which are being rolled out in the northwest region for investigating patients with suspected meningitis. This follows previous work that showed patients were not having appropriate testing done.(16)

Those classed as having suspected bacterial meningitis can be treated with broad spectrum antibiotics in accordance with local policies and/or the British Infection Association Guidelines (17). Virological investigations will not be performed, but they will remain in the study for the comparative analyses of different pathogens, and disease burden, as described below.

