6.2 Summary of Investigations

		All patients	Controls	Aseptic Meningitis	HSV Meningitis	Suspected BM
Sample	Test					
CSF	Opening Pressure	X				
	Microscopy and Culture	X				
	Protein	X				
	Glucose	X				
	CSF Viral PCR panel			x		
	Meningococcal/ Pneumococcal PCR +/- 16S PCR					X (If microscopy /culture negative.)(according to local protocol)
	4.5ml CSF for genomics	X (if consented to)				
3-5ml CSF for DNA sampling	X(if consented to)					
Blood	FBC	X				
	Clotting	X				
	U and E's	X				
	LFTs	X				
	CRP	X				
	Glucose	X				
	Blood Cultures	X				
	Serology	X				
	HSV type specific serology				X	
	HIV serology			X	X	X
HSV type specific serology (at 6 months).				X (If initial type specific serology negative)		
4.5ml EDTA blood for proteomics (SST)	X (if consented to)					
18.5ml for genomics	X(if consented to)					
18ml for DNA sampling	X(if consented to)					
Throat swab	Enterovirus PCR			X		
Stool/rectal swab	Enterovirus PCR			X		
Lesions (oral, skin, genital)	HSV PCR, VZV PCR			X		
Vesicle Fluid (if present)	HSV, VZV, enterovirus and parechovirus PCR			X		
Self taken genital swab (see text)	HSV PCR			X	X	

 Samples to be taken over and above what would be routine practice.

All samples may be stored (if consented to), anonymously, for future research studies.

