- There are also ethical issues with regard to requesting genital swabs from patients. These will be requested from those who have genital signs or symptoms but also from some asymptomatic patients. The reason for taking from asymptomatic patients is to assess if there is a relationship between asymptomatic genital shedding of HSV-2 and HSV-2 meningitis. In order to ascertain the importance of this a control group is also needed. The asymptomatic patients will be asked to take their own genital swabs which will lessen any embarrassment or distress and maintain dignity. If any of the swabs from the asymptomatic patients are positive for HSV they will be informed of this and advised to visit their local sexual health clinic. The relationship between HSV-2 meningitis and sexual health will be sensitively explained by the responsible clinician.
- Ethics of potential genetic analysis - the potential for identification of genetic variants could be associated with disease risk. While this information could possibly improve lives of individuals, providing information about low risk common variants that are not clinically relevant and have been identified using techniques that are not clinically validated may be harmful. To date, genetic research and analysis indicates that risk profiles generated by common, moderate and low risk genetic variants do not provide sufficient discrimination to warrant individualised prevention or treatment for complex diseases. The clinical utility of single, common, low-penetrance genes is therefore very limited. Given that the clinical implications of genetic profiles are unknown at the population and individual level and that these methods are being used for research purposes and have not been validated in the clinical setting, genetic data from the study **will not be disclosed to individual study participants.**

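### The 6.7 schedule limits the self-taken genital swab in lesion-free patients to those with HSV-positive CSF, while 6.1 and table 6.2 extend it to the whole aseptic group

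*Protocol*

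**What the plan says.** Four places in the Protocol bear on this swab.

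- **Section 6.1, Baseline Tests.** Patients with proven HSV meningitis who report no genital lesions are asked to swab themselves. The request is then widened: "In order to find out if there is a link between genital HSV infection and undiagnosed aseptic meningitis", the study will also ask "all patients in the aseptic meningitis" group. One exception follows: "If a patient lacks capacity genital swabs will NOT be taken unless clinically indicated".
- **Section 6.2, Summary of Investigations.** The row for the self-taken swab carries a mark under Aseptic Meningitis and another under HSV Meningitis, and refers the reader to the text. It has no mark under Controls or Suspected BM.
- **Section 6.7, Schedule.** For patients with no reported or documented genital lesions, the row reads "Self taken genital swab for HSV if CSF positive for HSV". The task is assigned to the research nurse and the patient, and the post-LP cell is marked as applying where appropriate. A separate row covers swabs of visible lesions and sets no condition on the CSF result.
- **Section 9.1, Ethical Considerations.** Some asymptomatic patients are swabbed to relate asymptomatic HSV-2 shedding to HSV-2 meningitis. The section adds: "In order to ascertain the importance of this a control group is also needed".

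The amendment list in section 16 records no narrowing of the swab to HSV-positive patients, so the 6.7 wording is not explained by a later change.

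**The concern.** The 6.7 row and section 6.1 cannot both be followed for an aseptic patient who has no lesions and whose CSF is HSV-negative. Section 6.1 asks that patient for a swab and 6.7 does not.

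This is the patient on whom the 6.1 question depends. Undiagnosed aseptic meningitis, by its meaning, has no HSV found in the CSF. The same patients are the only lesion-free comparison group for which table 6.2 plans this swab. A swab not taken during the acute illness cannot be recovered by any later analysis.

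There is also a milder risk. If some sites follow 6.1 and others 6.7, the comparator swabs come only from the first kind of site. Any difference in shedding between HSV and other aseptic patients is then mixed with differences between sites.

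**Working it through.** **1. Who is eligible for the self-taken swab under each section**

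| Patient without genital lesions, with capacity | 6.1 | Table 6.2 | 6.7 |
|---|---|---|---|
| HSV meningitis (CSF HSV-positive) | yes | yes | yes |
| Aseptic, CSF HSV-negative | yes | yes | no |
| Defined Controls (4 or fewer leukocytes) | not asked | no mark | no |

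The sections differ in the second line only. The where-appropriate marking in 6.7 does not close the gap, because the row states its own condition and that condition is a CSF result. The lesion row does not close it either, because a swab of a visible lesion does not measure asymptomatic shedding.

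**2. The Protocol's own case numbers (section 7.2)**

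Inputs: 18 aseptic cases over 3 months in 10 hospitals, projected to one year and 31 centres. The HSV-2 share of aseptic cases is 17%.

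- Aseptic: 18 × (12/3) × (31/10) = 223.2. The Protocol states 223, so this reproduces.
- HSV-2: 223 × 0.17 = 37.9. The Protocol states 38, so this reproduces.

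**3. What the two rules mean on those numbers**

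Let h be the number of HSV-1 CSF positives among the aseptic cases. Section 7.2 does not give it.

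- Eligible under 6.1 and 6.2: up to 223.
- Eligible under 6.7: 38 + h, because the row's condition is HSV of either type.
- Asked under 6.1 but not under 6.7: 223 − (38 + h) = 185 − h.
- Lesion-free, CSF HSV-negative comparators under 6.7: 0, by the wording of the row and whatever h is.

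All non-zero counts are upper limits, before refusals, patients with lesions and patients lacking capacity. The Protocol gives no shedding rates and no sample size for this comparison, so no power is calculated here.

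**The case against.** The strongest reply is that nothing ranks the schedule above sections 6.1 and 6.2. Table 6.2 is the place where samples are assigned to diagnostic groups. It marks both groups and points to the text, and the text is explicit. The schedule is also not a complete sampling guide: it has no row for HIV serology or for the repeat HSV serology, and its stool row does not carry the restriction to aseptic patients. This stands to the extent that the loss is conditional. It occurs where the 6.7 row is followed, and it is only an inference that nurses work from that row. But the Protocol states no order of precedence either, and the row gives a specific instruction to named staff.

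A reader might infer several stronger things that the Protocol does not support:

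- *Undiagnosed aseptic patients would have no genital sample at all.* They would if they had lesions, since lesion swabs do not depend on the CSF result. What is lost is the swab in lesion-free patients.
- *Exactly 38 would be swabbed and 185 would not.* HSV-1 positives lie within the 185 and would be eligible under 6.7.
- *The undiagnosed group numbers 223 − 38 − 18 − 58 = 109, and none would be swabbed.* That figure is only what remains after HSV-2, VZV and enterovirus. It can include HSV-1 and other identified causes.
- *These are expected counts for the present study.* They project one year in 31 centres. The protocol summary now gives 35–45 sites and an extension to 5 years.

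The control group in 9.1 is also ambiguous. Section 5.1 defines Controls as patients with 4 or fewer leukocytes, and table 6.2 does not mark this swab for them. If 9.1 means those patients, correcting the 6.7 row alone would not supply them. Finally, asymptomatic shedding is not named among the objectives or the outcomes in 7.1, and no sample size rests on it.

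**Conclusion.** The contradiction is real and should be corrected. Where 6.7 is followed, lesion-free aseptic patients with HSV-negative CSF contribute no swab. The 6.1 question then cannot be answered for asymptomatic shedding, and the HSV group has no aseptic comparator. Where practice differs between sites, the comparison is confounded with site.

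On the section 7.2 projection, eligibility falls from up to 223 aseptic patients to about 38 plus the unstated HSV-1 cases. These counts show the proportions only.

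The conclusion rests on the wording of four sections and on the absence of any amendment that narrows the sampling. How many sites follow the schedule cannot be known from the Protocol. The question is exploratory: the prevalence of viral meningitis and the contribution of each virus do not depend on it.

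**What to change.** Reconcile the 6.7 row with 6.1, table 6.2 and 9.1.

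- **If the 6.1 question is kept:** let the 6.7 row cover the aseptic group without genital lesions, not only CSF HSV-positive patients, and repeat the capacity exception there. State in 9.1 which patients form the control group, since table 6.2 does not mark this swab for the defined Controls.
- **If the question has been dropped:** say so in 6.1, 6.2 and 9.1.
- **For swabs already collected:** record which patients were asked, by site, so that shedding proportions use those patients as the denominator.

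The change to the schedule is one row, plus a clarifying sentence in 9.1. It adds no new procedure, because 6.1 and 9.1 already describe the sampling and its rationale. Sites that have been following 6.7 would collect more swabs than they do now.

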6.8 SUB-STUDIES

6.8.1 Qualitative study on outcomes important to patients.

We will take a selection of participants (c. 20) with proven herpes meningitis and follow them up with a semi-structured questionnaire to generate a hypothesis on what outcomes should be evaluated with respect to viral meningitis. Help will be sought for this from the department of public health and policy in the University of Liverpool. In order to do this consent will be taken from all patients to allow future contact.

Amendment 14 (6/5/2014) – In addition to recruiting patients who have been enrolled in the UK Meningitis study for the qualitative study I will also utilise links with the Meningitis Research Foundation (MRF). Often patients contact the MRF following an admission to hospital and are keen to take part in research. Currently this can only happen if the hospital they were in happens to be part of the study. However, for the qualitative study they could be interviewed without being part of the rest of the study. I will utilise the MRF and any patients recommended to me via them. I will not include any patients who directly approach me by other means but only through the MRF.

6.8.2 Retrospective study to calculate the prevalence of viral meningitis in the NW of England

In addition to our prospective study, in order to corroborate our results we will also be asking all centres in the North West to participate in a retrospective study.

All laboratories will be asked to provide retrospective data on CSFs they have received in the preceding 2 years from patients over the age of 16. Data to be collected will be:

- Age
- Gender
- CSF
 - o WCC
 - o Percentage lymphs
 - o Percentage neuts
 - o Percentage other
 - o RCC
 - o Pathogen identified (if any)
- Clinical diagnosis from notes (if not available from the laboratory system).

Most of this data should be easily obtainable from the laboratory information system (LIS) and shouldn't take longer than 10mins per patient.

This data will then be compared with population data – found on the census website or the SHA's website – in order to determine the incidence. We will also be able to compare trends in incidence over the years and with our prospective study.

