5 ENROLMENT

5.1 Screening

Screening criteria

- a) Over 16 years of age
- b) Suspected meningitis

Patients will be screened from participating hospitals when they have suspected meningitis (see definitions).

They will be allocated a screening number (including the site number) e.g. 01001 for site number 01, screening number 001.

They can be considered for inclusion in the study either by the admitting clinical teams (on clinical suspicion of meningitis), or by the diagnostic microbiology services (when they receive a CSF sample for analysis).

E.g.

Screening point 1:

A clinician identifies a patient that meets the inclusion criteria.

Screening point 2:

A laboratory identifies a CSF sample that is received in the microbiology department. The patient can then be screened for eligibility with regard to the inclusion criteria and clinically suspected meningitis.

Enrolment should occur within the same admission as the above tests are done.

A screening register or log will be required at each site and reasons for non-inclusion will be listed in the screening log. Screening log will be kept at site and at coordinating centre.

Definitions

SUSPECTED MENINGITIS

Illness for 3 weeks or less with:

Headache and one or both of:

- neck stiffness
- photophobia

*except for those with very sudden onset severe headache (defined as no pain to maximal pain within one minute).

OR

Other patients with symptoms in whom the clinician feels a lumbar puncture is needed to diagnose/exclude meningitis

MENINGISM

Headache with neck stiffness and/or photophobia

CSF ≤ 4 leukocytes per ml of CSF**.

(NB some of these patients may have positive microbiology/virology)

ASEPTIC MENINGITIS

Suspected Meningitis (as above), AND

Negative Cerebrospinal fluid (CSF) microscopy and culture for bacteria (or negative PCR for bacteria if on antibiotics prior to CSF sampling), AND

CSF white cell count of 5-1000 leukocytes per ml of CSF** (with a lymphocyte predominance unless total leucocyte count < 20)

and a CSF / Plasma glucose ratio of $> 40\%$ (if paired glucose taken).

WITH NO IMPAIRMENT OF CONSCIOUSNESS

(NB this group may be further subdivided into infective and non infective causes. If there are significant numbers of migraine in this group then they may also be separated out for purposes of analyses.)

PROVEN VIRAL MENINGITIS

Suspected meningitis, AND

CSF white cell count of >4 leukocytes per ml of CSF**

Positive CSF PCR for viral pathogen (or intrathecal antibody).

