7.2 Sample Size

Based on previous retrospective epidemiological studies (Kupila et al and Michael et al) we expect to see the following number of cases.

58	No meningitis	Bacterial Meningitis	Aseptic meningitis	HSV-2 meningitis	VZV	Enterovirus
1066	682	160	223	38	18	58

This is based on Michael et al's study(36) finding 217 patients with suspected CNS infection over a 3 month period in 10 hospitals in the North West of England. 18 of these patients had aseptic meningitis, 13 had purulent meningitis and 55 just had meningism. I have, therefore, extrapolated that there were 86 patients with suspected meningitis (although this may be an underestimate.) Only 5 of the patients with aseptic meningitis had viral PCRs done and 1 of these (20%) was positive for HSV-2. Although this is clearly a small number it is similar to Kupila et al(5) who found 17% of their aseptic meningitis cases had HSV-2. They also found 26% with enterovirus and 8% with VZV.

I have extrapolated the numbers from Michael et al's study to calculate the expected numbers over a year and in 31 centres. I have calculated the expected prevalence of different viruses from the data in Kupila's study.

It is likely that this is an underestimate as it is based on retrospective data.

Using the HES data(3) there were 2741 finished consultant episodes of viral meningitis in England in 2009-2010. Based on the fact that the North West region has 13% of England's population (Census data) we could expect up to 356 cases of viral/aseptic meningitis in one year.

For this type of study approximately 50 patients are needed as a minimum. For comparisons between diagnostics groups (eg herpes meningitis versus bacterial meningitis), a minimum of 25 patients would be needed in each group to have 90% power to show a

difference of one standard deviation in the measure of interest, allowing for approximately 10% drop out. We are likely to have at least this number of patients with herpes meningitis, and probably many more.

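### The retrospective North West data list omits whether each viral PCR was done and the sample date, so virus-specific incidence and trends are confounded by testing uptake

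*Protocol*

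**What the plan says.** Protocol section 6.8.2 gives the purpose of the sub-study: "in order to corroborate our results we will also be asking all centres in the North West to participate in a retrospective study". Laboratories are to supply "retrospective data on CSFs they have received in the preceding 2 years". The section then lists the data to be collected: age, gender, CSF white cell count, lymphocyte, neutrophil and other percentages, red cell count, "Pathogen identified (if any" and the clinical diagnosis, taken from the notes where the laboratory system does not hold it. These data are to be set against population figures to obtain incidence, and the section adds: "We will also be able to compare trends in incidence over the years and with our prospective study".

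Four other places bear on this:

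- **Section 5.1:** proven viral meningitis requires a raised CSF white cell count and a positive CSF PCR for a virus, or intrathecal antibody.
- **Section 6.1:** in the prospective study, aseptic cases receive a viral CSF panel plus enterovirus PCR on throat and stool or rectal samples. The section acknowledges past under-testing and mentions "lumbar puncture packs which are being rolled out in the northwest region for investigating patients with suspected meningitis".
- **Section 6.9.2:** laboratory practice varies, and some laboratories run only the tests the clinician asks for.
- **Section 7.2**, on the earlier regional series: "Only 5 of the patients with aseptic meningitis had viral PCRs done and 1 of these (20%) was positive for HSV-2". That series had 18 aseptic cases.

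**The concern.** The primary outcome (section 7.1.1) is the prevalence of viral meningitis in the North West and each virus's contribution to it. The retrospective study is offered as outside support for that result. On the listed items, a record with no pathogen may be a case tested and found negative, or a case never tested. The two cannot be separated afterwards, because test status is not requested.

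The prospective cohort is tested to a stated panel, whereas the retrospective records reflect whatever was requested at the time. A difference between the two in proven-viral or virus-specific incidence could come from disease, from testing, or from both. The same holds for a difference between years, and without a sample date the listed items cannot assign a case to a year at all. A reader could then take agreement as corroboration, or disagreement as a change in epidemiology, when neither inference is secure.

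**Working it through.** **Step 1. Reproduce the protocol's case table (section 7.2).** The inputs are a 3-month series in 10 hospitals, scaled to 12 months and 31 centres. The factor is (12/3) × (31/10) = 12.4.

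- Suspected meningitis: 86 × 12.4 = 1066.4 (stated 1066)
- No meningitis: 55 × 12.4 = 682.0 (stated 682)
- Bacterial: 13 × 12.4 = 161.2 (stated 160)
- Aseptic: 18 × 12.4 = 223.2 (stated 223)

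The virus shares from the Finnish adult series are applied to 223:

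- HSV-2: 17% gives 37.9 (stated 38)
- VZV: 8% gives 17.8 (stated 18)
- Enterovirus: 26% gives 58.0 (stated 58)

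The table reproduces closely enough to use. Section 6.8.2 gives no figure of its own.

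**Step 2. Proportion tested in the earlier regional series.** 5/18 = 27.8%, with an exact (Clopper-Pearson) 95% CI of 9.7% to 53.5%.

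**Step 3. Effect on recorded cases.** If testing is unrelated to aetiology, recorded viral cases = expected viral cases × proportion tested. Expected HSV-2, VZV and enterovirus cases under full testing are 38 + 18 + 58 = 114, which is 114/223 = 51% of aseptic cases.

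| Proportion tested | Recorded of 114 | Undercount (1 / proportion) |
|---|---|---|
| 9.7% (lower limit) | 11 | 10.3-fold |
| 27.8% (5/18) | 32 | 3.6-fold |
| 53.5% (upper limit) | 61 | 1.9-fold |

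True incidence is the same in every row.

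**Step 4. Apparent change between periods.** Hold true incidence constant and let uptake rise from 27.8% to an assumed 60% to 90%. Recorded incidence is then multiplied by 0.60/0.278 = 2.16 up to 0.90/0.278 = 3.24. The end values are assumptions; the protocol gives no uptake for either period.

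**Step 5. What test status would add.** In the earlier series HSV-2 is 1/18 = 5.6% of all aseptic cases if every untested case is counted as negative, and 1/5 = 20% if the untested are assumed positive at the tested rate. With test status recorded, the result can be reported as that range with 28% tested. With only the listed items, 5.6% is all that can be reported, with nothing to show that 13 of the 18 were never tested. One positive patient is too few to estimate HSV-2 itself; the example shows only the mechanism.

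**The case against.** A reader might infer that the retrospective study cannot corroborate anything. The documents do not support that. Cell count, differential and clinical diagnosis do not depend on PCR, and the aseptic definition in section 5.1 rests largely on the CSF count. Section 7.2 itself uses a combined viral/aseptic figure. An approximate aseptic incidence can be formed and compared with the prospective count, although the glucose ratio, symptoms, consciousness and prior antibiotics are not listed. This objection stands and limits the point to proven-viral and virus-specific results.

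A reader might also infer that any trend would reflect testing and not disease. That is not shown. The packs are being rolled out and are used only where in place, which bears on the prospective period and is no evidence that uptake rose within the retrospective two years. The supportable word is confounded.

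The size is fragile. The 5/18 comes from another, small series, and uptake in the planned window is unknown. This stands, which is why the interval is shown.

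On dates, laboratories must select samples from a two-year window, so dates exist at extraction. That makes the omission cheap to mend, but the list still does not request them.

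It is tempting to add that repeat lumbar punctures will be counted twice, or that patients with ventricular devices will enter the count. The documents do not establish either. The request concerns CSFs, but it also speaks of patients and of time per patient, and the clinical diagnosis may reveal device cases. No effect of either can be shown.

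It might be said that this belongs in an analysis plan. Methods of comparison may, but the items to collect are set out in the protocol, and no later analysis can recover test status that was not requested.

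Finally, this is a supporting sub-study. The prospective estimate does not depend on it, and section 7.2 concedes that its own figures are probably underestimates because they rest on retrospective data. Both limit the severity, but neither makes the virus-specific comparison interpretable.

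**Conclusion.** The point holds in limited form. As listed, the section 6.8.2 data cannot separate untested from negative cases and cannot place a case in a year. Retrospective proven-viral and virus-specific incidence, its trend, and its comparison with the prospective cohort are therefore confounded by testing uptake.

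At the earlier series' uptake of 28% (about 10% to 54%), the undercount would be about 3.6-fold (1.9 to 10). This assumes that the untested resemble the tested and that the earlier uptake carries over to the planned window; the documents establish neither. Even the favourable limit is nearly a twofold error.

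The syndrome-level comparison of aseptic meningitis survives in approximate form. This should be changed before the data are requested, but it does not threaten the prospective estimate.

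**What to change.** Add to the section 6.8.2 list:

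- the sample date;
- for each virus, PCR not done, negative or positive;
- a pseudonymised patient identifier, so that repeat samples can be recognised.

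State that the main comparison with the prospective study is aseptic incidence defined by cell count, with the same definition applied to both datasets as far as the listed items allow.

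Report virus-specific incidence only with the proportion tested and a range. One end takes all untested cases as negative; the other takes them as positive at the tested rate, stated as an assumption. Do not present raw pathogen counts as corroboration or as a trend. The same applies to positivity among the tested alone: where laboratories test on request, the tested are selected, and positivity can move as testing widens even if incidence is constant.

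The cost is a few more items per record, from the laboratory systems already being queried, and a small protocol amendment. Virus-specific incidence becomes a range instead of a single figure.
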